604 distance (6 meters) and at near (33 cm) as outlined in the *IXT7 Procedures Manual*. The
605 examiner will be required to be masked to treatment group. Testing time is approximately 2-
606 4 minutes.
- 607 4. Cycloplegic Refraction: A cycloplegic refraction will be done prior to enrollment and only if
608 clinically indicated thereafter. After administration of eye drops, it typically takes 30 minutes
609 to achieve cycloplegia, and testing time for refraction of both eyes is in the range of 2 to 10
610 minutes.
- 611 5. Suppression Testing: Suppression will be assessed using the Office Suppression Test which
612 grades the level of suppression while tropic on a 4-level scale. Testing will be performed at 6
613 meters as outlined in the *IXT7 Procedures Manual*. Testing must be performed by a pediatric
614 ophthalmologist, pediatric optometrist, or certified orthoptist. The examiner will be required
615 to be masked to treatment group. Testing time is approximately 3-5 minutes.
- 616 6. Retinal Correspondence Testing: In children 6, 7, or 8 years old at time of randomization,
617 retinal correspondence status will be assessed by the Hering-Bielschowsky after-image test,
618 using a PEDIG-provided flash unit. Correspondence will be assessed when aligned and when
619 tropic to record overall status as either:

620 Testing must be performed by a pediatric ophthalmologist, pediatric optometrist, or certified
 621 orthoptist as outlined in the *IXT7 Procedures Manual*. The examiner will be required to be
 622 masked to treatment group. Testing time is approximately 3-5 minutes.

623

624 7. Control of IXT: Assessment of IXT control will be performed using the Office Control
 625 Scale³⁵ at both distance (6 meters) and near (1/3 meter), fixating an accommodative target.
 626 Testing must be performed by a pediatric ophthalmologist, pediatric optometrist, or certified
 627 orthoptist as outlined in the *IXT7 Procedures Manual*. The examiner will be required to be
 628 masked to treatment group. Testing time is approximately 3-5 minutes.

629 The scale below applies to both distance and near test distance separately.

630 Intermittent Exotropia Control Scale

631 5 = Constant Exotropia

632 4 = Exotropia > 50% of the 30-second period before dissociation

633 3 = Exotropia < 50% of the 30-second period before dissociation

634 2 = No exotropia unless dissociated, recovers in >5 seconds

635 1 = No exotropia unless dissociated, recovers in 1-5 seconds

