864 of 1.8 points (95% CI, 1.4 to 2.5 points) after 8 weeks. Therefore, we estimate that a mean
865 change of 1.45 points after 3 months of full-time patching in the current study is reasonable for
866 an active treatment.

867 **Sample Size Estimation:**

868 The study will be powered for the primary objective.

869 Assuming a mean change in distance control score after 3 months of 0.30 points in the
870 observation group and 1.45 points in the full-time patching group; we estimate that the true
871 difference is 1.15 points between full-time patching and observation at 3 months.

872

873 **Hypothesis Test for Objective – FT vs OBS at 3 Months:**

874 Assuming a pooled standard deviation of 1.5 points for change in distance control score after 3
 875 months, and a correlation of 0.30 between distance control score at baseline and change from
 876 baseline after 3 months, a total sample size of 68 participants (34 per group) completing the 3-
 877 month outcome has 90% power with a type I error rate of 5% to evaluate whether there is a
 878 treatment group difference between FT patching and OBS if the true difference is 1.15 points,
 879 Table 2. Accounting for 5% loss to follow-up after 3 months, a total of 72 participants (36 per
 880 treatment group) will need to be enrolled. The overall number of participants with an interocular
 881 difference in distance VA of 2 logMAR lines (10 letters on E-ETDRS for patients ≥ 7 years old) will be
 882 limited to 14.

883 **Table 2: Total Sample Size for Difference in Mean Distance Control Score**

Standard Deviation of Change in Distance Control (points)	Treatment Group Difference for Outcome of Mean Change in Distance Control (points)		
	0.85	1.00	1.15
1.4	106	78	60
1.5	122	90	68
1.6	138	100	78

884 Cells indicate N for the overall study (two treatment groups combined with a ratio of 1:1), using a 2-sided test with
 885 alpha 0.05, from an analysis of covariance model evaluating a difference between treatment groups for mean change
 886 from baseline in distance control, controlling for baseline distance control.

887

888 If the true effect with FT patching is as small as 0.99, the study would still have 80% power to
 889 reject the null in favor of a difference (and 1.05 with 85%).

890 **7.4 Interim Monitoring**

891 Given the short duration of the primary outcome at 3 months, there will be no formal interim
 892 analysis for stopping the study early for efficacy or futility.

893 **7.5 Analysis Datasets**

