- 922 • Repeat the above sensitivity analysis using observed data from participants who completed
- 923 the 3-month visit within the protocol window (\pm 2 weeks).

924
 925 Sensitivity Analysis #3 (ITT minus participants with IOD 2 logMAR lines at enrollment):

- 926 • The overall number of participants with an interocular difference in distance VA of 2
- 927 logMAR lines (10 letters on E-ETDRS for patients \geq 7 years old) will be limited to 14.
- 928 • The ITT analyses as described in 7.5 will be repeated excluding these participants.

929
 930 **7.7 Analysis of the Secondary Endpoints**

931 All secondary analyses described below will use observed data only. Treatment group
 932 comparisons specified in the sections below will be controlled using false discovery rate (FDR)
 933 at the 5% probability level to account for the multiple outcomes. For all secondary analyses, an
 934 estimate of difference between the groups will be reported at each timepoint along with an FDR-
 935 adjusted confidence interval and p-value unless otherwise specified. Further details about the
 936 secondary analyses below will be part of a separate statistical analysis plan (SAP).

937 **7.7.1 Near Control**

938 At 3 months, near control will be evaluated similarly to the distance control primary analysis
 939 (section 7.6) using ANCOVA models that adjust for the mean near control score at baseline and
 940 the near angle by PACT at baseline.

941 Additionally, the proportion of participants with 2 or more points improvement in control from
 942 baseline will be compared between the treatment groups at 3 months using a two-sided Barnard's
 943 test with calculation of a two-sided FDR-adjusted confidence interval on the difference in
 944 proportions. This will be done separately for control at distance and near.

945 **7.7.2 Angle of Deviation**

946 At 3 months, a two-sided comparison of magnitude of the angle of deviation by PACT will be
 947 performed between treatment groups using an ANCOVA model, which adjusts for baseline
 948 PACT. The treatment group difference and an FDR-adjusted confidence interval will be
 949 calculated. The analysis will be completed separately at distance and at near.

950 Additionally, the proportion of participants with improvement of distance and near angle greater
 951 than the test/retest variability⁶³ will be compared between the treatment groups at 3 months using

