2.3 Multiple Imputation of Missing Values

The multiple imputation will be performed for missing data using Monte Carlo Markov Chain (MCMC) modeling, which includes the mean distance control score at baseline and the change in mean distance control score from baseline to the 3-month (or early outcome) visit, and the distance PACT at baseline. Imputed values will be limited to the range of possible changes in mean control score (-5.0 to 3.0), using options available in the imputation software. If necessary, observed 3-month control scores may be transformed to achieve (or approximate) the normal distribution prior to imputing, and then backtransformed for analysis.

- The multiple imputation will be performed separately by treatment group to account for potential
- interaction between the treatment groups and the follow-up distance control scores. The number of
- imputations will be set to 100. Missing baseline data are not expected for distance PACT angle; however, if
- such missing data occurs, it will be imputed in the MCMC model so that participants with missing baseline
- data are included in the analysis.

3 Secondary Analyses

- All secondary analyses described below will use observed data only without imputation for missing data.
- Only data from 3-month outcome visits that occurred within the analysis window (or data from early 3-
- month outcome visits) will be included in analysis. For all secondary outcomes, the data will be tabulated,
- and means and standard deviations, or numbers with the outcome and percentages, will be calculated for
- each of the treatment groups. The false discovery rate will be controlled at 5% using the two-stage step-up
- procedure¹ to account for multiple secondary outcomes. Reported p-values and confidence intervals will
- incorporate the FDR adjustment.

120121

112

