3.3 Level of Suppression

- The proportion with each level of suppression (negligible, mild, moderate, or dense, as indicated on the
- completed follow-up worksheet) by treatment group at 3 months will be tabulated. The median and
- interquartile range for each group will be calculated and the distributions of suppression levels compared

between treatment groups at 3 months using the exact non-parametric Wilcoxon rank-sum test and twosample Hodges-Lehmann estimator.

4 Exploratory Analyses

Exploratory analyses will describe the distribution of the outcome, or change in outcome from baseline, within each treatment group and estimate treatment group differences and 95% confidence intervals (CIs), unless specified otherwise, with the purpose of identifying hypotheses for further study. All exploratory analyses will use observed data only without imputation for missing data. Only visits occurring within the analysis window will be included. As these are exploratory analyses, no adjustment for multiplicity will be made to confidence intervals and no p-values will be reported.

Continuous outcomes will be described using mean, standard deviation, and 95% CIs. Median and interquartile range (IQR) will also be reported if the outcome distribution is asymmetric. Treatment group differences and 95% CIs will be estimated using an ANCOVA model with adjustment for baseline level of the outcome. ANCOVA is relatively robust to violations of normality and homoscedasticity⁴; however, if ANCOVA model estimation of treatment group differences is of questionable validity due to violation of normality or other assumptions, actions to mitigate the violation will be undertaken. For example, for homoscedasticity violations, an ANCOVA model allowing the treatment groups to have different variances may be used and/or large outliers may be winsorized to the 5th and 95th percentiles of the overall outcome distribution (with treatment groups combined). In cases where winsorization of outliers is used, descriptive statistics for the treatment groups will be based on the outcome distribution after winsorization, and winsorized values will be noted in table/figure footnotes. Results of mitigated and original analyses will be compared for consistency, and results of both analyses reported if there are substantial differences.

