262263264

Scatterplots, with Spearman correlation coefficients and 95% confidence intervals, will be generated to illustrate the relationship between the total number of hours patched and each outcome listed below for those with ODM data:

265266

- 267 1. Distance control score
- 268 2. Near control score
- 269 3. Distance angle of deviation
- 270 4. Near angle of deviation
- 5. Suppression Score (0=negligible, 1=mild, 2=moderate, 3=dense)
 - 6. Convergence fusional amplitudes
- 273 7. Divergence fusional amplitudes
 - 8. Symptom Survey Score
 - 9. PedEyeQ score (each domain)

275276277

272

274

The relationship between the total number of hours patched and the suppression score will be illustrated using a boxplot, rather than a scatterplot.

278279280

281

282

283

284

285

286

Patching adherence is categorized by the study coordinator as excellent, good, fair, or poor based on inspection of the patching calendar and discussion with the parent. This data will be tabulated for the 3-month visit, as will the reasons for any major deviations. Descriptive statistics and a boxplot for total number of hours patched as recorded with the ODM by level of patching adherence based on parent report will be obtained.

6 Association of Retinal Correspondence Testing to Other Outcomes

The relationship between retinal correspondence response and each of the following outcomes within each treatment group will be evaluated at 3 months:

287 288 289

290

291

293

294

295

296

- 1. Distance control score
- 2. Near control score
 - 3. Distance angle of deviation
- 292 4. Near angle of deviation
 - 5. Suppression Score (0=negligible, 1=mild, 2=moderate, 3=dense)
 - 6. Convergence fusional amplitudes
 - 7. Divergence fusional amplitudes
 - 8. Diplopia by parental assessment (dichotomized as in section 4.5)
 - 9. PedEyeQ score

Normal retinal correspondence will be defined as correspondence status marked "normal" both when aligned and tropic, while anomalous retinal correspondence will be defined as correspondence status marked "abnormal" when aligned or tropic (or both).

301 302 303

304

305

306

307

308

309

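### The only between-group estimate planned for suppression, a Hodges-Lehmann shift on a four-level grade, moves in whole grades, and for moderate effects its interval will usually end exactly at 0 when the Wilcoxon test is significant

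*SAP*

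**What the plan says.** Protocol 4.1 (item 5) describes the Office Suppression Test as one that "grades the level of suppression while tropic on a 4-level scale". SAP 3.3 sets out the output: "The proportion with each level of suppression (negligible, mild, moderate, or dense, as indicated on the" follow-up worksheet, by arm, plus the median and interquartile range per arm. The arms are then compared "using the exact non-parametric Wilcoxon rank-sum test and twosample Hodges-Lehmann estimator". That is the only between-group estimate named for this endpoint. SAP 3.3 gives no numeric coding, but SAP sections 5 and 6 do: "Suppression Score (0=negligible, 1=mild, 2=moderate, 3=dense".

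SAP 3.3 names no interval. One is implied by two general rules. Protocol 7.7 promises, unless otherwise specified, that for every secondary analysis an "estimate of difference between the groups will be reported at each timepoint along with an FDR"-adjusted confidence interval and p-value. SAP section 3 says "The false discovery rate will be controlled at 5% using the two-stage step-up" procedure, and that "Reported p-values and confidence intervals will" carry that adjustment. Protocol 7.7.3 names only the exact Wilcoxon test.

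**The concern.** The Hodges-Lehmann estimate is the median of all pairwise differences between a patched and an observed child. On a continuous scale it can express an effect of any size. On four integer grades it cannot: the same moderate true effect will be reported as no shift in one trial and as a full grade in the next. The order-statistic interval is read from the same integers, so a significant Wilcoxon result will often be printed beside an interval such as −1 to 0.

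This endpoint deserves a better estimate. Protocol 1.4 describes patching as anti-suppression therapy and says that few data show suppression changing with patching. Protocol 1.7 says this study would supply such evidence. The SAP keeps suppression as one of only three secondary outcome sections.

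**Working it through.** **Arm size.** Inputs from Protocol 7.3: difference 1.15, SD 1.5, correlation 0.30, 90% power, two-sided 5%.
- Residual SD = 1.5 × √(1 − 0.30²) = 1.431.
- Normal formula: 2 × (1.960 + 1.282)² × 1.431² / 1.15² = 32.5, so 33 per arm. The noncentral-t version gives 34 per arm, matching "a total sample size of 68 participants (34 per group"), and reproduces all nine cells of Table 2.
- 68 / 0.95 = 71.6, so 72 enrolled, as stated.

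The documents state no figure for the suppression analysis itself.

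**What the estimator and interval can show with 34 per arm.** There are 34 × 34 = 1,156 pairwise differences, each an integer from −3 to 3 (negative favours patching).
- Estimate: the average of the 578th and 579th ordered differences. It reaches −1 only if at least 579 pairs (50.1%) have the patched child strictly lower.
- 95% limits: C = 578 − 1.96 × √(1,156 × 69 / 12) = 578 − 1.96 × 81.53 = 418. The limits are the 418th and 739th ordered differences. The upper limit falls below 0 only if at least 739 pairs (63.9%) are strictly lower on patching.

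**What the test needs, in an assumed example.** Patching (.40, .30, .20, .10) v observation (.20, .30, .30, .20) for grades 0 to 3.
- Patched child strictly lower: .40 × .80 + .30 × .50 + .20 × .20 = .51. Ties: .08 + .09 + .06 + .02 = .25. Mann-Whitney probability = .51 + .25/2 = .635.
- Null SD of that probability: 81.53 / 1,156 = .0705. Pooled grades (.30, .30, .25, .15) give a tie factor √(1 − .073) = .963, so the SD is .0679. Significance starts near .5 + 1.96 × .0679 = .633.
- With 25% ties, .633 corresponds to .633 − .125 = 50.8% of pairs strictly lower.

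So the test becomes significant at about 51% strictly lower, while the interval does not clear 0 until about 64%. Between those two points the report is a significant p-value with an interval ending at 0. The true value, 51%, also sits almost on the 50.1% boundary between an estimate of 0 and one of −1.

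Simulation agrees. Power is about 51 to 52%. The estimate is 0 in 44 to 46% of all trials and −1 in nearly all the rest. The interval ends at 0 in 91 to 92% of significant trials. Among significant trials the estimate is 0 in only about 1 to 2%.

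**Varying the assumptions.** Six assumed observation-arm distributions were crossed with proportional odds ratios, using exact Wilcoxon p ≤ 0.05, 34 per arm and an unadjusted 95% interval.

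| Odds ratio | Mean power | Interval ends at 0, share of significant trials: mean (range) | Estimate is 0, share of significant trials: range |
|---|---|---|---|
| 2 | 32% | 98% (96–100%) | 2–52% |
| 2.5 | 51% | 97% (92–99%) | 1–54% |
| 3 | 65% | 93% (85–98%) | 0–48% |
| 4 | 85% | 85% (68–97%) | 0–41% |
| 6 | 97% | 67% (36–91%) | 0–34% |
| 10 | about 100% | 44% (about 8–12% up to 86%) | 0–24% |

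- Half-grade estimates appeared in at most about 1.5% of significant trials.
- A tie-corrected test-inversion interval lowered the mean shares by 0 to 2 points.
- With 30 per arm the means were 93% (odds ratio 3) and 86% (odds ratio 4).
- A 99% interval, used as a stand-in for FDR widening, ended at 0 more often: 86 to 99% at odds ratio 4.
- An estimate of 0 in over 40% of significant trials occurred only where many children are already at the lowest grade. With 70% v 40% negligible, the estimate was 0 in 41 to 42% of significant trials and the interval ended at 0 in 96 to 97%.

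**Zero is an end, not an interior point.** For the upper limit to exceed 0, at least 418 pairs (36.2%) would have to be strictly higher on patching. In the example, significance needs strictly lower to exceed strictly higher by 2 × (.633 − .5) = .266, which makes at least 62.8% lower and leaves about 1% for ties. That is not realistic on four grades, and simulation found no such case.

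**The case against.** A reader might infer that estimate and test contradict each other in about 90% of significant trials. The documents do not support that as a property of the plan: they give no distribution, effect size or interval method. For larger assumed effects the share drops. With (.50, .25, .15, .10) v (.15, .25, .30, .30) it is 58 to 59%, and with (.55, .25, .12, .08) v (.10, .20, .30, .40) it is 12%. Contradiction is also too strong a word. An interval of −1 to 0 keeps the direction, and in settings like the worked example the estimate is almost always −1 when the test is significant.

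A reader might also infer that the Hodges-Lehmann estimate is invalid here. It is not. The median pairwise difference is well defined on grades, it is a conventional companion to the Wilcoxon test, and it is in grade units. Only its reading as a constant shift needs a location-shift model.

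Two further points stand. SAP 3.3 specifies no interval, whereas 3.1 and 3.2 name a method for theirs, so the interval examined here is the usual one and not a stated one. And the proportion at each grade, the median and the interquartile range are all reported, so no reader would have the shift alone.

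What remains is that the sole between-group estimate is too coarse to convey the size of a moderate effect. The tabulation softens this but does not supply a between-group estimate with an interval.

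**Conclusion.** The point holds in a limited form. That the estimate can only be a whole or occasional half grade, with interval limits that are essentially whole grades, follows from the four-level coding and needs no simulation. How often the interval ends at 0 in significant trials depends on assumptions: about 85 to 97% on average for odds ratios of about 2.5 to 4, and about 8% to over 99% across all scenarios tried. These figures assume 34 per arm, proportional odds and an unadjusted 95% order-statistic interval.

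The exact Wilcoxon test remains valid with ties. Its error rate, its power, the FDR decision and the primary endpoint are unaffected. Only the effect estimate for this one secondary outcome, and its interval, are weak. The change is worth making because it is nearly free and the endpoint bears on the proposed mechanism of patching.

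**What to change.** In SAP 3.3, replace the Hodges-Lehmann shift with the Mann-Whitney probability: the probability that a patched child has a lower suppression grade than an observed child, with ties counted half. Report it with a confidence interval, name the interval method (for example a DeLong-type interval), and apply the FDR adjustment used for the other secondary outcomes. Keep the exact Wilcoxon test, the grade tabulation, and the median and interquartile range.

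This probability is a rescaling of the Wilcoxon statistic already planned, so test and estimate describe the same quantity. In simulation its unadjusted interval excluded 0.5 in at least 99.9% of Wilcoxon-significant trials.

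The cost is one phrase in the SAP and a standard computation. The downside is that the estimate is a probability and not in grade units, which the tabulated proportions cover.

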4.1 Proportion with Anomalous Retinal Correspondence

For those able to perform the test, normal retinal correspondence will be defined as correspondence status marked "normal" both when aligned and tropic, while anomalous retinal correspondence will be defined as correspondence status marked "abnormal" when aligned or tropic (or both). This outcome will be analyzed as a binary outcome.

4.2 Convergence and Divergence Fusional Amplitudes

The distribution of fusional convergence amplitude (blur point, break point, and recovery point) and fusional divergence amplitude (break point and recovery point) will be described by treatment group using medians and interquartile ranges and compared between treatment groups at 3 months using the exact Wilcoxon rank sum test. When no blur is reported for fusional convergence, the break point will be used for analysis.

